# Secondary outcomes:

- 1) Proportion of CCDT positives that sought help at TPO as a result of the CCDT (quantitative)
- 2) Acceptability and appropriateness of the CCDT (qualitative)
- 3) Feasibility of using the CCDT at scale (qualitative)
- 4) Attitudes towards mental health problems (qualitative)

Mixed-effects Poisson regression using a log link with clustering of zones within settlements and repeated measures within zones will be used to estimate the ratio of monthly mental health services utilization from the pre-CCDT to post-CCDT implementation periods. Utilization will be standardized using an offset of the log of the child population size estimate in each zone. CCDT implementation, time, and the interaction between CCDT and time since cross-over will be included as fixed effects. The effect of CCDT will be reported as an incidence rate ratio (IRR, 95% CI). Settlement and zone will be included as a random intercept. Heterogeneity across zones and settlements in time trends and treatment effects will be explored as random effects using the interaction between settlement/zone with time and CCDT implementation. If the assumptions of

Poisson regression are not fulfilled, we will estimate a mixed-effects negative binomial model. All analyses will be conducted using Stata, Version 17.

In addition, descriptive within-group analyses will be conducted to assess the proportion of children and adolescents detected by a gatekeeper using the CCDT that utilized TPO's mental healthcare during the entire project period. Among that group we will also assess the number of children and adolescents that initiated treatment and completed treatment.

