# Sample Size

Sampling takes place at zone level. The number of children and adolescents that will be detected and that will utilize TPO's services/service points per month within each zone will be determined as primary outcome of this evaluation. Using existing utilization data, we estimated the number of zones required to detect a 20% difference in utilization rates pre- to post-CCDT implementation with at least 90% power. Among the zones for which we had existing utilization data available (n=26 zones), we estimated a mean of 17.1 initial encounters with mental healthcare per month per zone (SD=20.1, Median=11.8, IQR=4-24). We conservatively estimated utilization to equal zero in the two zones for which we had missing information. We also conducted a sensitivity analysis by imputing utilization rates for the two zones with missing data by selecting a random number from a Poisson distribution that reflected available utilization data. The intraclass correlation of utilization among zones within a settlement was estimated to be low (ICC=0.115).

Following methods developed by Woertman and colleagues [24], we estimated the minimum sample size required for parallel-groups randomized controlled trial and multiplied that value by the design effect for a stepped-wedge trial over a range of steps to estimate the number of zones required for this study [25]. Twenty-eight zones with seven steps would provide greater than 90% power to estimate a 20% difference in utilization between pre-CCDT and post-CCDT implementation. CCDT will be introduced in four zones per step (i.e., one-month each in length) and monthly utilization data will be collected from each zone the day before the next step.

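### The primary model lets the CCDT effect change with time since cross-over, but the plan reports one CCDT IRR without saying at what exposure time; read plainly, it is the effect at cross-over, not the pre-to-post effect

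*Protocol*

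**What the plan says.** The model paragraph of the Protocol's Statistical Analysis plan (printed under Secondary outcomes, but describing the primary utilization analysis) states its aim as to "estimate the ratio of monthly mental health services utilization from the pre-CCDT to post-CCDT implementation periods". It specifies a mixed-effects Poisson model and says that "CCDT implementation, time, and the interaction between CCDT and time since cross-over will be included as fixed effects". The next sentence on the result is "The effect of CCDT will be reported as an incidence rate ratio (IRR, 95% CI").

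The Sample Size section uses the same pre-to-post language: "we estimated the number of zones required to detect a 20% difference in utilization rates pre- to post-CCDT implementation", and "Twenty-eight zones with seven steps would provide greater than 90% power to estimate a 20% difference in utilization between pre-CCDT and post-CCDT implementation". The method is a parallel-group sample size, and the authors "multiplied that value by the design effect for a stepped-wedge trial over a range of steps".

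The Protocol does not say at which time since cross-over the IRR is evaluated, whether it is averaged over exposure months, how time since cross-over is coded, or how the interaction is to be reported.

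**The concern.** With an interaction between CCDT and time since cross-over there is no single CCDT effect. There is a different IRR for each month of exposure. The coefficient labelled CCDT is the log IRR where time since cross-over is zero. The stated target and the power statement both concern the post-CCDT period as a whole, so the three parts of the plan do not describe the same quantity unless the effect is constant, and including the interaction allows that it may not be.

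This bears on the primary result. A tool whose effect grows could show an IRR near 1, and a tool whose effect fades could show an inflated one. Leaving the contrast and the coding open also allows the exposure time of the headline IRR to be chosen after the data are seen.

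**Working it through.** **1. The plan's own sample size.** Inputs from the Sample Size section: mean 17.1 and SD 20.1 encounters per zone per month (a 20% difference is 0.20 x 17.1 = 3.42), ICC 0.115, seven steps. Two-sided alpha 0.05 is assumed, because it is not stated.

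- Parallel-group size: 2 x (1.96 + 1.282)^2 x 20.1^2 / 3.42^2 = 726 per arm, 1452 in total.
- Stepped-wedge design effect with k = 7 steps, t = 1 measurement per step, b baseline months, n = 17.1 and rho = 0.115: DE = [1 + rho(ktn + bn - 1)] / [1 + rho(ktn/2 + bn - 1)] x 3(1 - rho) / [2t(k - 1/k)].
- b = 1: (16.617 / 9.734) x 0.1936 = 0.3305. Zones = 1452 x 0.3305 / 17.1 = 28.1; power with 28 zones 0.90.
- b = 2: DE = 0.3075, 26.1 zones, power 0.92.

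The stated 28 zones therefore reproduce, but for one constant effect.

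**2. What the CCDT coefficient estimates.** With e = months since cross-over, log IRR(e) = b1 + b2 x e. So exp(b1) is the IRR at e = 0 only. Training takes place in the week before the step (Training and supervision community gatekeepers), so e = 0 is the first CCDT month if that month is coded 0. If it is coded 1, exp(b1) is an extrapolation to before that month.

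**3. How much of the data lies at e = 0.** Four zones cross each month. Seven steps plus one baseline month make 8 periods; the Clusters section gives 9 months, so 9 is shown as well.

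| Periods | Baseline months | CCDT zone-months at e = 0, 1, 2, ... | Total | Mean e | Share at e = 0 |
|---|---|---|---|---|---|
| 8 | 1 | 28, 24, 20, 16, 12, 8, 4 | 112 | 2.0 | 25% |
| 9 | 1 | 28, 28, 24, 20, 16, 12, 8, 4 | 140 | 2.4 | 20% |
| 9 | 2 | 28, 24, 20, 16, 12, 8, 4 | 112 | 2.0 | 25% |

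**4. Illustration.** The trajectories are assumed; the Protocol gives none. Fix the IRR at e = 2.0 at 1.20.

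- Build-up from 1.00: monthly factor (1.20/1.00)^(1/2) = 1.095; IRR at e = 6 is 1.73. Reported exp(b1) = 1.00, or 1.00/1.095 = 0.91 if the first month is coded 1.
- Decay from 1.44: monthly factor (1.20/1.44)^(1/2) = 0.913; IRR at e = 6 is 0.83. Reported exp(b1) = 1.44, or 1.44/0.913 = 1.58 if coded 1.
- With 9 periods and one baseline month, the same slopes give 1.24 and 1.16 at the mean exposure of 2.4; exp(b1) is unchanged.

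A noise-free Poisson fit with zone and month effects returned exactly 1.00 and 1.44 in all three layouts.

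**5. Dropping the interaction.** The same data fitted with a constant effect (equal zone sizes):

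| Layout | Build-up | Decay |
|---|---|---|
| 8 periods | 0.94 | 1.54 |
| 9 periods, one baseline month | 0.92 | 1.58 |
| 9 periods, two baseline months | 0.97 | 1.50 |

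No value lies near the effect at mean exposure; the build-up even appears as a decrease.

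**6. Precision of the averaged contrast.** Assumptions not in the Protocol: between-zone variance of 0.9 on the log scale (log(1 + (20.1/17.1)^2) = 0.87) and dispersion phi from 1 (pure Poisson) to 3. Ranges cover the three layouts and linear or categorical exposure time. Power is for a true IRR of 1.20.

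| Quantity | SE of log IRR, phi = 1 | Power, phi = 1 | Power, phi = 3 |
|---|---|---|---|
| Constant-effect model | 0.054-0.057 | 0.89-0.92 | 0.46-0.50 |
| CCDT coefficient at e = 0 | 0.054-0.058 | 0.89-0.92 | 0.45-0.50 |
| Average over CCDT zone-months | 0.065-0.082 | 0.61-0.81 | 0.26-0.38 |

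**The case against.** The strongest reply is that the Protocol nowhere says the bare coefficient will be reported. A combination of terms computed after fitting, or exposure time centred at its mean, would fit the wording and give the averaged effect, and a separate SAP might define either. That stands in part. A reader might infer that the plan commits itself to the first-month effect; the text does not go that far. But this section is itself titled a statistical analysis plan and fixes both the model and the reported quantity, and the ordinary reading of a CCDT effect from that model is the CCDT coefficient. More than a detail is left open, because that coefficient differs from the plan's own target whenever the interaction is not zero.

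A second reply is that the consequences depend on the trajectory. This also stands. It is tempting to conclude that a working tool would be reported as ineffective. The documents do not support that as a certainty: no trajectory is given, the interaction would be estimated and could reveal a build-up or decay, monthly trends are also to be examined, and under a constant effect the coefficient and the average agree.

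Third, the supervision schedule might be read as evidence of a build-up. It is not: sessions are bi-weekly for the first two months and monthly afterwards, which points at least as much to an early effect. The need for a child to be detected and then to attend points the other way. The direction is unknown.

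**Conclusion.** The point holds as a mismatch between the stated target and the reported quantity. The target and the power statement concern a pre-to-post ratio; the model makes the CCDT coefficient an effect at exposure time zero; and no sentence connects the two. In the assumed examples the reported IRR is 1.00 or 1.44 (0.91 or 1.58 under the other coding) where the IRR at mean exposure is 1.20. The size depends on the assumed log-linear trajectories and is nil if the effect is constant. That the coefficient and the average are different quantities does not depend on the trajectory, nor on whether there are 8 or 9 periods.

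A reader might also infer that the sample size is miscalculated. It is not: 28 zones reproduce under the stated inputs. The limitation is that the figure applies to a constant effect, not to an average taken from the interaction model.

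**What to change.** Keep the exposure-time term and add to the Statistical Analysis plan:

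- the coding of time since cross-over, with the value given to the first CCDT month;
- the primary IRR as the effect averaged over the CCDT zone-months of the roll-out: exp(b1 + s x b2) with its 95% CI, s being the mean months since cross-over with the first CCDT month coded 0 (2.0 with 8 periods, or with 9 periods and two baseline months; 2.4 with 9 periods and one baseline month). The average over exposure-month indicators is an alternative that does not assume a log-linear change;
- the number of baseline months, so that s is fixed in advance;
- the interaction as a secondary result.

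The programming cost is small: a few lines of text and one linear-combination command in Stata. The real cost is precision. Under pure Poisson counts the standard error of the log IRR is roughly 0.07-0.08 for the average against about 0.055 for the CCDT coefficient, and larger with overdispersion. The claim of more than 90% power should be restated for the chosen contrast with its variance assumptions shown; on the assumptions used here it is 0.61-0.81 without overdispersion and lower with it. Averaging over roll-out zone-months is one defensible choice among several; what matters is that one is fixed before the data are analysed.

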# **Secondary objectives**

- 1. To examine the proportion of help-seeking (i.e., mental health care utilization) following pro-active case detection using the CCDT (independent of between-group comparisons).
- 2. To examine implementation outcomes in terms of the acceptability, appropriateness, and feasibility of using the CCDT at scale for community gatekeepers.
- 3. To examine community gatekeepers' attitudes towards mental health problems after the introduction of the CCDT, relative to rates pre-training.

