#### DATA COLLECTION AND PROCESSING

#### Description of data collected

Both quantitative and qualitative data will be collected.

Quantitative data

Quantitative data will be collected at two levels:

- 1) Detection data Gatekeepers will be provided with a logbook in which they will record the information about the detection (see Annex 4.2). A unique study ID will be created for each new case, this code will be linked to the gatekeepers' initials and cannot be traced back to the individual. The following information will be collected by gatekeepers:
  - o Study ID
  - Child's demographic information: age, gender, status (refugee/host), village, zone and settlement of residence
  - Contact details family
- Version of the CCDT used (i.e., the CCDT vignette that matched their observations)
- o Date of detection and engagement
- Date of verbal consent/assent obtained

This data will be collected in the zones where the CCDT is introduced, from the moment that the gatekeepers start using the CCDT, until the end of the project duration (i.e., April, 2023).

- 2) Service utilization (TPO) routine data will be collected at TPO for all clients seeking care. An anonymized client code will be assigned and used as the only identifier. The following variables will be collected in the Case Registration Form (see Annex 4.1):
  - Client ID
  - Demographic information: age, gender, status (refugee/host), village, zone and settlement of residence
  - Referral type: through CCDT or routine
    - This will be obtained through the referral card handed out by the gatekeeper using the CCDT (i.e., 'someone in the community approached me, handed out a referral card and encouraged me to seek help here')
  - Date of intake
  - Type of visit: new, re-entry or recurring/maintenance visit.
  - Mental health diagnosis
  - Service or type of treatment provided by TPO, or referral made

If treatment was initiated and completed.

This data will be collected from the beginning of the study in all zones, until the end of the project duration (i.e., April, 2023). A study specific data extraction sheet will be developed which will be used to collect all the information according to the primary and secondary outcomes.

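### Detection and service data both end in April 2023 with no follow-up allowance, so truncation lowers the help-seeking proportion and the count of treatment completers

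*Protocol*

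**What the plan says.** Secondary objective 1 in the protocol is "To examine the proportion of help-seeking (i.e., mental health care utilization) following pro-active case detection using the CCDT", without any between-group comparison. Outcome measures and Statistical Analysis plan also list the same proportion under the primary outcome.

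The analysis is at the end of the Secondary outcomes text of the Statistical Analysis plan section. It is a descriptive share of detected children "that utilized TPO's mental healthcare during the entire project period". The next sentence adds: "Among that group we will also assess the number of children and adolescents that initiated treatment and completed treatment".

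Description of data collected sets the dates. Detection data run "from the moment that the gatekeepers start using the CCDT, until the end of the project duration (i.e., April, 2023". For the TPO service data it says: "This data will be collected from the beginning of the study in all zones, until the end of the project duration (i.e., April, 2023". The service form also holds the completion field, "If treatment was initiated and completed". The dates needed for a time-based analysis are on the two forms: "Date of detection and engagement" in the logbook and "Date of intake" in the case registration form.

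Outcome measures and Table 1 define the proportion without a time window. No section closes detection earlier for this analysis, follows TPO attendance for longer, sets a minimum observation time or provides for censoring.

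**The concern.** The denominator grows until the last day on which the numerator can be observed. A child handed a card at the end of April 2023 counts as detected but has almost no chance of being counted as a TPO user. Completion suffers twice, because both the delay to intake and the course of treatment must fit before the cut-off.

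The proportion has no comparator, so its absolute value is the answer to research question 2 and nothing cancels the loss. The completion count would be read as a measure of what happens after referral, and it is the more exposed of the two.

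**Working it through.** The protocol states no expected proportion or completion count, so there is no figure to reproduce.

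**Inputs from the protocol**
- 28 zones, four per one-month step (Sample Size), so 28/4 = 7 steps.
- Order of introduction fixed before October 2021 (Clusters).
- Both data streams end in April 2023 (Description of data collected).
- 67% of accurately detected cases reached care with the adult tool in Nepal (Rationale and background information). It is used here only as an illustrative eventual attendance; the protocol sets no target.

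**Assumptions**
- First step in November 2021 and a constant detection rate to the end of April 2023. The seven sequences then have T = 18, 17, 16, 15, 14, 13 and 12 months of detection; the sum is 105 and the mean is 15.
- Delay from detection to first TPO contact is exponential with mean m months, for those who eventually attend.
- Treatment lasts a fixed L months.

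**Detections with short follow-up.** The share with less than w months is 7w/105: 6.7%, 13.3% and 20% for w = 1, 2 and 3.

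**Help-seeking under the plan.** Captured share = Σ[T − m(1 − e^(−T/m))] / ΣT. For m = 1 the exponential terms are negligible, giving (105 − 7)/105 = 93.3%, and 0.933 × 67% = 62.5%.

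| Mean delay (months) | Captured | A true 67% is reported as | Loss (points) |
|---|---|---|---|
| 0.25 | 98.3% | 65.9% | 1.1 |
| 0.5 | 96.7% | 64.8% | 2.2 |
| 1 | 93.3% | 62.5% | 4.5 |
| 2 | 86.7% | 58.1% | 8.9 |
| 3 | 80.2% | 53.7% | 13.3 |

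With one month less detection in every zone (17 down to 11 months), the 1-month row becomes 92.9% captured and 62.2% reported, so the start date matters little.

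**Completion under the plan.** Replace T by T − L in the numerator only. At m = 1:
- L = 2: (105 − 14 − 7)/105 = 84/105 = 80% of eventual completers captured.
- L = 3: (105 − 21 − 7)/105 = 77/105 = 73%.
- L = 4: (105 − 28 − 7)/105 = 70/105 = 67%.

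**Two possible remedies for help-seeking, on the same 67%.**
- *Minimum follow-up of 3 months, visits counted to the cut-off:* captured share = 1 − m·Σ(e^(−3/m) − e^(−T/m)) / Σ(T − 3), with Σ(T − 3) = 84.
- *90-day cap on visits, every child followed for 90 days:* captured share = 1 − e^(−3/m).

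| Mean delay (months) | Plan | Minimum follow-up, no cap | 90-day cap |
|---|---|---|---|
| 0.5 | 64.8% | 67.0% | 66.8% |
| 1 | 62.5% | 66.7% | 63.7% |
| 2 | 58.1% | 64.5% | 52.1% |
| 3 | 53.7% | 61.0% | 42.4% |

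The minimum follow-up rule is closer to 67% than the plan at every delay tested. The cap is better than the plan only when delays are short.

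**The case against.** **The window belongs in a separate analysis plan.** Such detail is often left there, and counting over the whole project can be read as a contrast with the 9-month stepped-wedge period, which already lengthens follow-up for most children. The second part stands. But the protocol does more than stay silent: it fixes the period and gives both data streams the same end, and that rule applied as written is truncated.

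**The size is assumed.** This stands. Care is offered at zone level, including at home or school, and gatekeepers receive airtime to follow up cases, so delays of weeks are plausible. The help-seeking loss would then be 1 to 2 points.

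**The net direction is not shown.** This also stands. Families who decline consent, and children with no caregiver available, are not logged. If they attend less often, their absence raises the proportion. The numerator, based on an intake question, may also include children who received a card but were never logged. Only the truncation component is certain to be downward.

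**Readings the documents do not support.** A reader might infer that late entrants are formally scored as non-completers. The plan asks for a number and defines no completion denominator, so the count is low but nobody is so classified. A reader might also expect unfair comparison with the 67% from Nepal. That is an adult-tool figure, the protocol does not make it a benchmark, and its follow-up is not described. Nor is the difference between sequences important: at a 1-month delay, 94.4% is captured in the first and 91.7% in the last, and this outcome is not compared between groups.

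**Conclusion.** The point holds for truncation alone. As written, the rule lowers the help-seeking proportion and the completer count, and no other section offsets it. With 12 to 18 months of detection per zone, constant detection, exponential delay and 67% eventual attendance, help-seeking loses about 1 to 5 points for mean delays of 0.25 to 1 month, and about 9 to 13 points at 2 to 3 months. Completion is the more exposed figure: a fifth to a third of eventual completers are missed for assumed courses of 2 to 4 months at a 1-month delay. Delay and course length are assumptions throughout.

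A reader might infer that the trial's main result is at risk because the proportion is also listed under the primary outcome. It is not: the incidence rate ratio comes from monthly utilization counts and does not use this proportion. This is a cheap improvement to a descriptive analysis.

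**What to change.** In the descriptive paragraph of the Statistical Analysis plan section:

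1. Name the data cut-off. Restrict the help-seeking denominator to children detected at least a stated time before it (for example 90 days), and count their visits up to the cut-off. Alternatively, report a Kaplan-Meier cumulative proportion from detection date to intake date, censored at the cut-off. A 90-day cap alone should not stand in for eventual help-seeking, because it answers a different question and reports less than the present plan when delays are long.
2. Report completion with its denominator, only among CCDT-referred children whose intake was at least one treatment-course length before the cut-off, and state the length used.

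**Cost.** The denominator shrinks slightly: 20% of detections fall in the last three months under the assumptions above. The first item also needs logbook entries matched to TPO records; without matching, cards handed out late would still feed the numerator. The protocol says the logbook ID cannot be traced to the individual, and Description of quantitative data flow and entry system mentions entering only the number of cases. However, gatekeepers record names, and a master list links IDs to names, so matching looks feasible. The sponsor should confirm this and that individual detection dates will be entered. The completion restriction needs only the TPO form, which holds referral type, intake date and completion.
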